Trapezio – metacarpal arthroplasty:

comparison of ARPE[®] prosthesis with the literature

PROTOCOL NUMBER (Study ID): ORTHO.CR.E16

PROTOCOL VERSION: V1.0 dd 12 Nov 2012

GENERAL INFORMATION

Study Sponsor: BIOMET Global Supply Chain Center B.V. [name] The Netherlands

TITLE	Trapezio-metarcarpal arthroplasty: a comparison of ARPE prosthesis with the literature
SHORT TITLE	Arpe prospective study
DESIGN	Non-controlled, prospective cohort study in single centre
STUDY DURATION	2013- 2020
STUDY CENTRE	Single centre in Belgium
POPULATION	Inclusion of 100 subjects at single centre
PRIMARY Research objectives	The primary objective is to compare functional outcome at 3 years after trapezio-metarcarpal arthroplasty with trapeziectomy and trapeziectomy with ligament reconstruction and tendon interposition. Literature values obtained by a recently published meta analysis ¹ will be used.
SECONDARY Research Objectives	Secondary objectives are: - to compare functional outcome at 1 and at 5 years after trapezio-metarcarpal arthroplasty with trapeziectomy and trapeziectomy with ligament reconstruction and tendon interposition - to determine pre- and postop HR QOL - Incidence of RLL at each f/up time point. Literature values from the same meta analysis ¹ will be used.
OUTCOME Measures	Patients will be assessed at preoperatively, and at 1, 3 and 5 years postoperatively. Outcomes as described by Li et al ¹ will be measured: grip strength, tip pinch strength, key pinch strength, pain, occurrence of adverse events, hand function.
Follow-up time	Patients will be part of a longitudinal follow-up program with follow-ups at 1, 3, 5 years.
Enrollment time	2 Years

STATISTICS

SAMPLE SIZE CALCULATION

Based on a publication from Davis et al² we expect the standard deviation in the study population for key pinch, tip pinch, and grip strength to be 0.82, 1.65 and 10.3, respectively. Setting alpha at 0.05 and beta at 0.10, and assuming a MIREDIF (Minimally Relevant Difference)of 0.5 x Standard Deviation, an attrition rate of 10%, and data to be approximately normally distributed, the required sample size will be 96 (\approx 100) subjects.

STATISTICAL PROTOCOL

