Continuous variables (e.g. age) will be summarized using the mean and standard deviation (SD). If the distribution of measurements is asymmetrical, the median and the interquartile range will be provided. For ordinal and nominal data proportions should be employed. Inferential statistics will be based on the unpaired t-test, or the Mann-Whitney test, depending on normality of the data.

REFERENCES

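### The 3-year comparison as written uses only subjects with a 3-year value, leaving their lost peers' earlier measurements unused and the ARPE mean open to modest attrition bias in either direction

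*Combined protocol and SAP*

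**What the plan says.** In the combined protocol and SAP, the STATISTICAL PROTOCOL section gives descriptive summaries and then one sentence on inference: "Inferential statistics will be based on the unpaired t-test, or the Mann-Whitney test, depending on normality of the data".

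The rest of the design is in the GENERAL INFORMATION table:

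- Design: "Non-controlled, prospective cohort study in single centre".
- Visits: "Patients will be assessed at preoperatively, and at 1, 3 and 5 years postoperatively".
- Primary objective: "The primary objective is to compare functional outcome at 3 years after trapezio-metarcarpal arthroplasty with trapeziectomy", with or without ligament reconstruction and tendon interposition. The comparator is "Literature values obtained by a recently published meta analysis".
- First secondary objective: "to compare functional outcome at 1 and at 5 years after trapezio-metarcarpal arthroplasty", against the same source.

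Under SAMPLE SIZE CALCULATION the plan sets "Setting alpha at 0.05 and beta at 0.10", a relevant difference (MIREDIF) of half a standard deviation, and "an attrition rate of 10" percent, arriving at 96 subjects, rounded to 100. Attrition is mentioned nowhere else. The documents contain no missing-data rule, imputation, repeated-measures model, comparison of lost with retained subjects, or sensitivity analysis.

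**The concern.** An unpaired test at year 3 takes one value per subject, so a subject without a 3-year value contributes nothing to it. For most such subjects the study will already hold a pre-operative value of the same outcome, and often a 1-year value. The named method has no means of using them for the 3-year mean.

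That matters only if the subjects lost differ from those retained. If they do, the observed mean no longer estimates the mean of everyone operated on, and the 10% allowance in the sample size does not help: it restores precision and leaves bias untouched. With no concurrent arm followed under the same procedures, the design gives no assurance that similar loss on the other side would balance it. What is at stake is a shift in the primary estimate, and a type I error above the stated 5%.

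**Working it through.** **1. The plan's own figure.** A two-sample, two-sided t-test with a difference of 0.5 SD, alpha 0.05 and power 0.90 needs 85.03, so 86 per group. Then 86 / 0.90 = 95.6, which rounds up to the stated 96. With 100 enrolled and 10% lost, 90 subjects have 3-year data.

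**2. Inputs for the bias.** From the plan: 10% loss, 0.5 SD relevant difference, alpha 0.05, 100 enrolled. Assumed, because the documents give no values:

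- correlation r between 1-year and 3-year values of 0.5 to 0.8;
- log-odds of loss before year 3 linear in the 1-year value, with odds ratio OR per SD worse, the intercept being set so that 10% are lost;
- normal values, scaled so that higher is better.

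**3. Bias of the observed 3-year mean.** Bias B = r × m, where m is the mean 1-year value, in SD units, among those retained. Numerical integration gives m:

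| OR per SD | m | B at r = 0.5 | B at r = 0.8 | B / 0.5 SD |
|---|---|---|---|---|
| 1.2 | 0.018 | 0.009 | 0.015 | 2–3% |
| 1.5 | 0.040 | 0.020 | 0.032 | 4–6% |
| 2 | 0.066 | 0.033 | 0.053 | 7–11% |
| 3 | 0.098 | 0.049 | 0.078 | 10–16% |

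With OR = 1 the bias is 0. If subjects doing well are the ones lost, the same figures apply with a minus sign.

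Using the SDs in the plan, 0.033 to 0.078 SD is 0.03 to 0.06 for key pinch (× 0.82), 0.05 to 0.13 for tip pinch (× 1.65) and 0.34 to 0.80 for grip (× 10.3).

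**4. Effect on type I error.** Two-sided error = Φ(−1.96 + B/SE) + Φ(−1.96 − B/SE).

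- Comparator assumed to have 86 patients: SE = √(1/90 + 1/86) = 0.151. For OR 2 to 3, B/SE runs from 0.22 to 0.52 and the error from 5.6% to 8.1%. For OR 1.2 to 1.5 it is 5.0% to 5.5%.
- Comparator taken as a fixed number: SE = √(1/90) = 0.105. For OR 2 to 3, B/SE runs from 0.31 to 0.74 and the error from 6.1% to 11.5%.

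The 86 is the per-group size that reproduces the plan's 96. It is not a count of literature patients, which the documents do not give.

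**5. Using the earlier values.** In a simulation of 8,000 trials (n = 100, r = 0.7, OR = 3, 10% missing at year 3), the observed-case mean had bias 0.068 SD and root mean square error 0.125 SD. A likelihood estimate using the pre-operative and 1-year values had bias 0.000 and root mean square error 0.104. Loss here depends only on an observed value, so the zero bias is what missing-at-random implies.

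**6. When that assumption fails.** If loss depends on the 3-year value itself (10% loss, OR 2 to 3, correlation 0.5 to 0.7), observed-case bias is 0.065 to 0.099 SD. Using the earlier values leaves 0.028 to 0.068 SD, or 43 to 69% of it. About one third to just over one half is removed.

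**The case against.** The strongest reply is that the effect is small and its direction unknown. At the planned attrition even strong dependence moves the mean by at most 0.08 SD against a relevant difference of 0.5 SD, and mild dependence by 0.01 to 0.03 SD. Nothing in the documents says that subjects doing poorly are the ones lost. This stands, and it sets the weight of the point.

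A reader might infer that the 1-year data of lost subjects are thrown away. The documents do not support that: the 1-year comparison is a secondary objective and those values enter it. They are only not used for the 3-year mean. That each visit is tested separately is itself an inference, from the unpaired test, the visit-specific objectives and the silence on missing data.

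A reader might also infer that any bias in the ARPE mean passes in full into the comparison. If the literature values too come from patients who completed follow-up, part of it could cancel. The documents do not say, so the plan can neither rely on this nor exclude it.

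Finally, the mixed model is not a complete cure. It relies on missing-at-random and approximate normality, whereas the plan allows a rank test for non-normal data. A subject lost before year 1 offers only a pre-operative value. An observed-case sensitivity analysis does not test departures from missing-at-random either, because it omits the same subjects. These limits stand. Even so, the model's assumption is weaker than the one the present plan needs for an unbiased mean, namely that loss is unrelated to function.

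**Conclusion.** The point holds as a modest, conditional weakness. As written, the 3-year comparison rests on observed cases only, although earlier values of the same outcomes will exist for subjects lost later.

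At 10% loss, with between-visit correlation 0.5 to 0.8 and loss logistic in the 1-year value, the bias in the ARPE mean is 0.01 to 0.03 SD at odds ratios 1.2 to 1.5 and 0.03 to 0.08 SD at odds ratios 2 to 3. At the higher odds ratios the two-sided type I error is about 5.6 to 8.1% with an assumed 86 comparator patients, or 6.1 to 11.5% with a fixed benchmark. All the loss-pattern inputs are assumptions.

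The documents do not support saying that the study will favour ARPE: the sign depends on who is lost, and there is no bias if loss is unrelated to function. Nor could attrition of this size produce a 0.5 SD effect by itself. The case for acting is that the remedy is cheap and best fixed before results are seen. Priority: between a minor suggestion and a change that should be made.

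**What to change.** Add one paragraph to STATISTICAL PROTOCOL:

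- For each continuous outcome, estimate the ARPE means at 1, 3 and 5 years from one mixed model for repeated measures, with visit as a categorical factor (pre-operative, 1, 3, 5 years), an unstructured covariance, and all operated subjects who have any value.
- Compare the model's 3-year mean and its standard error with the literature value for the primary objective, and the 1- and 5-year means likewise for the secondary one.
- Keep the observed-case comparison as a sensitivity analysis.
- Report pre-operative and 1-year values of subjects lost by year 3 beside those of subjects retained, so that the direction and strength of any selective loss can be seen.
- State that the model assumes missing-at-random and approximate normality.

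The cost is the wording and a standard model fit. No patients, visits or measurements are added and the sample size is unchanged. The model removes the bias under missing-at-random but only part of it if loss depends on the unseen 3-year value. If loss is unrelated to function, the gain is a few percent in precision at most. Outcomes that are not continuous, such as adverse events, lie outside this change.
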